### 5.1.1.4 Missing Data

General missing data handling conventions are summarized as follows:

**Table 5-3 Missing Data Handling by Endpoint Type**

Endpoint type	Timing	Missing Data Handling
Responder	Month 3 UCP	
 
• All subjects included (mITT population)
 
• Multiple imputation with 5 imputed datasets is applied to subjects with Month 3 LFS missing using the below model:  <math display="block">\text{Month 3 LFS} = \beta_0 + \beta_1 \text{ Baseline LFS} + \beta_2 \text{ Month 1 LFS}</math> 
 

Responder	Month 3 UCP	
 
• All subject included (mITT population)
 
• Last observation carried forward (LOCF) for subjects with Month 3 LFS missing, baseline value will be carried forward if no postbaseline value before Month 3
 
 
Last observation will be carried forward regardless of schedule/unscheduled visit or analysis window flag.

The above missing data handling conventions will only be used for sensitivity analysis of the primary effectiveness endpoint.

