STUDY DESIGN: 
This is a prospective, multicenter, randomized, no-treatment-controlled study to evaluate the safety and effectiveness of VOLBELLA with Lidocaine for lip enhancement in a Chinese population.
 
Subjects will be randomized at a 3:1 ratio either to have treatment with VOLBELLA with Lidocaine at the outset of the study (VOLBELLA with Lidocaine group, also referred to as the treatment group) or to have treatment delayed by 3 months (no-treatment control group). Treatment and safety assessments of a subject throughout the study will be performed by the same Treating Investigator (maximum 2 Treating Investigators per site), and effectiveness assessments will be performed by the same Evaluating Investigator. The Evaluating Investigator will remain blinded to treatment assignments throughout the duration of the study. Subjects randomized to the treatment group should undergo treatment on the same day as randomization. If initial treatment does not occur on the randomization day for subjects in the treatment group, it must occur within 30 days after screening. Subjects randomized to the no-treatment control group will attend study visits at months 1 and 3 of the no-treatment control period at which they will undergo effectiveness measures also performed at randomization. These measures include the Evaluating Investigator's assessment of the subject's lip fullness using the 5-point Lip Fullness Scale (LFS; 5 points: Minimal, Mild, Moderate, Marked, and Very Marked) and facial 3-dimensional (3D) imaging. [REDACTED]
 
[REDACTED]
 
[REDACTED] In addition, vital signs will be collected. After the completion of the control period, subjects randomized to the no-treatment control group will receive optional treatment for lip enhancement and follow the same schedule of visits and procedures in the treatment period as described below and in Table 1 for subjects randomized to the treatment group.
 
On the initial treatment day, the trained Treating Investigator will inject VOLBELLA with Lidocaine into the lips, as needed for lip enhancement. Allowable treatment areas are the vermilion body, vermilion border (including the Cupid's bow), and philtral columns. Prior to initial treatment, the Evaluating Investigator and the subject will rate the subject's lip fullness by using the LFS, and the Evaluating Investigator will rate the subject's philtral column definition by using a 5-point scale (Not Defined, Barely Defined, Somewhat Defined, Well-defined, and Very Well-defined). On day 30 after initial treatment, the Evaluating Investigator will again rate the subject's lip fullness and philtral column definition. Subjects may undergo an optional touch-up treatment at the day 30 visit after initial treatment, if the Treating Investigator assesses that optimal correction was not achieved. At each treatment visit, the subject will rate procedural pain on an 11-point scale immediately after receiving the injections, and the Treating Investigator will assess the ease of injection and the product moldability. Subjects will complete a safety diary for 30 days after each treatment and will complete a safety follow-up telephone call at 3 days after each treatment. Before treatment on each treatment day, the subject will undergo facial 3D imaging, which will also be performed 30 days after treatment.
 
Routine follow-up visits for safety and effectiveness will occur at 1, 3, and 6 months after the last treatment for both groups. At these visits, facial 3D imaging will be performed, [REDACTED]

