4.5 Treatment Allocation Ratio and Stratification

Subjects will be randomized at a 3:1 ratio either to have treatment with VOLBELLA with Lidocaine at the outset of the study (treatment group) or to have treatment delayed by 3 months (no-treatment control group). Randomization will be stratified by baseline LFS score (ie, LFS score rated as Minimal, Mild, or Moderate at the randomization visit by the Evaluating Investigator).

5. Study Population

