8.3 Hypothesis and Methods of Analysis

In general, descriptive statistics will be presented. Categorical variables will be summarized with frequency and percentage. Continuous variables will be summarized by number of subjects, mean, median, standard deviation, minimum, and maximum. Where appropriate, 2-sided 95% confidence intervals (CIs) for mean or proportion will be provided as part of the descriptive summary.

Unless otherwise noted, during posttreatment follow-up visits (for both the VOLBELLA with Lidocaine group and the no-treatment control group), baseline refers to the last evaluation prior to initial treatment; during the no-treatment period (for the no-treatment control group), baseline refers to the last evaluation prior to the month 1 visit.

No imputation for missing data will be performed. However, sensitivity analyses for the primary endpoint will be performed using applicable missing imputations to assess the potential effect of missing data.

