8.5 Sample Size Calculation

A sample size of 111 randomized subjects treated with VOLBELLA with Lidocaine and 37 randomized untreated control subjects will provide > 96% power to detect the superiority of VOLBELLA with Lidocaine over no treatment for responder rate at month 3. Responder rate is the percentage of subjects who show at least a 1-point improvement compared with baseline on the 5-point LFS based on the Evaluating Investigator's assessment of overall lip fullness. A 2-sided Fisher's Exact test with 5% significance level will be used to calculate the power, assuming responder rates of 79.0% for the VOLBELLA with Lidocaine group and up to 44.1% for the no-treatment control group at month 3 (based on interim data from Study [JULIDO-002](#)). The power calculation was performed using an Inequality Test for 2 Independent Proportion [Difference] procedure in PASS software (Version 2008). The planned sample size is considered to be adequate for evaluation of long-term (ie, 12-month) safety.

Allowing for attrition of 15% up to month 3 due to early discontinuations, missed visits, or out-of-analysis-window visits, 176 subjects will be randomized, with at least 132 subjects assigned to the VOLBELLA with Lidocaine group and approximately 44 subjects assigned to the no-treatment control group.

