#### 5.1.3.1 Primary Effectiveness Endpoint

The primary effectiveness analysis based on UCP is summarized in the following table. Subjects with baseline LFS score as assessed by EI of Minimal, Mild, or Moderate are enrolled in the study. A LFS (as assessed by EI) responder is defined as a subject with at least one grade improvement from baseline on 5-point LFS as assessed by EI.

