**Table 5-15 Primary Effectiveness Analyses**

Endpoint	Description	Timing	Methodology
LFS Responder as assessed by EI	Superiority of VOLBELLA with Lidocaine over no-treatment control  Number (%) of responders by treatment group (mITT population)	Month 3	Responder exact test

The primary effectiveness analysis will be performed based on the mITT population without any missing data imputation. For treatment subjects, assessments within window will be used. For control subjects who do not receive optional treatment, the assessments within month 3 window will be used. For control subjects who receive optional treatment, the assessments within month 3 window and before optional treatment will be used. Sensitivity analysis will be performed using missing data handling conventions as described in Section 5.1.1.4 as well as using PP population.

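### The multiple-imputation sensitivity model for the primary endpoint has no treatment-arm term, so it misstates the arm difference among imputed subjects unless Month 1 LFS carries the whole arm effect

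*SAP*

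**What the plan says.** SAP 5.1.1.4, Table 5-3, gives two ways to fill a missing Month 3 LFS score. One is last observation carried forward. For the other it says: "Multiple imputation with 5 imputed datasets is applied to subjects with Month 3 LFS missing using the below model". The model is then printed in full: Month 3 LFS equals an intercept, plus a coefficient times baseline LFS, plus a coefficient times Month 1 LFS.

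The table's footnote limits its use: "The above missing data handling conventions will only be used for sensitivity analysis of the primary effectiveness endpoint". SAP 5.1.3.1 confirms this from the other side: "The primary effectiveness analysis will be performed based on the mITT population without any missing data imputation".

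The purpose is set in Protocol 8.3: "sensitivity analyses for the primary endpoint will be performed using applicable missing imputations to assess the potential effect of missing data".

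The endpoint is a change in grade. SAP 5.1.3.1 says that a "responder is defined as a subject with at least one grade improvement from baseline on 5-point LFS as assessed by EI". SAP Table 5-2 then compares the two arms by responder rate difference, an exact interval and Fisher's exact test.

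**The concern.** The analysis that follows the imputation compares arms, but the imputation model ignores arm. A VOLBELLA subject and an untreated subject with equal baseline and Month 1 scores get the same predicted Month 3 score. That is right only if the arm adds nothing once Month 1 LFS is known, and nothing in the documents supports this.

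Allocation is 3:1 (Protocol 4.5), so the common regression is fitted mostly to treated subjects, and the imputed control rate is the one that moves most.

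A second gap sits beside this. The model type is not named (linear regression is the natural reading), and no rule turns an imputed value into one of the grades 0 to 4 that define a responder. This gap can put both arms' imputed responder rates far too low. It is a separate fault from the missing arm term.

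At stake is whether the analysis can do its job. It is the only model-based check on missing data; the others are LOCF and the PP population. As printed, a gap between it and the primary result could come from the model and not from the missing data.

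**Working it through.** **Inputs from the documents.** Month 3 responder rates 79.0% and 44.1%, 111 and 37 evaluable subjects, 15% attrition (Protocol 8.5); 132 and 44 randomized (Protocol 5.1); 3:1 allocation (Protocol 4.5). The difference is 79.0 − 44.1 = 34.9 points. SAP Table 5-24 prints 34.1%, which does not follow from its own two rates; 34.9 is used here.

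**The plan's own figure.** Exact enumeration of the 2-sided 5% Fisher test at 111 vs 37 and 79.0% vs 44.1% gives power 96.7%, in line with the stated > 96%.

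**Assumed inputs, none from the documents.**
- LFS change is −1, 0, +1 or +2; 20% of responders gain 2 grades; 15% of non-responders lose 1.
- Month 1 and Month 3 changes are linked by a Gaussian copula with latent correlation 0.5, 0.6 or 0.7 (observed 0.36–0.60) and 0.9 (observed 0.67–0.79). Near-zero correlation is left out because one Evaluating Investigator rates each subject throughout.
- Baseline Minimal/Mild/Moderate mixes are 20/40/40, 10/30/60 and 40/40/20.
- Month 1 is observed, and Month 3 is missing completely at random.

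**Step 1: the arm term alone.** For each baseline-by-Month 1 cell k, let f_a(k) be the share of arm a in the cell and r_a(k) its true Month 3 responder rate. A model without arm can at best reproduce the pooled rate

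p(k) = [0.75 f_V(k) r_V(k) + 0.25 f_C(k) r_C(k)] / [0.75 f_V(k) + 0.25 f_C(k)].

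The imputed rate in arm a is Σ f_a(k) p(k), and the share kept is the imputed difference divided by 34.9. No linearity or rounding enters. With arm in the model the share is 100% by construction.

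Example, latent correlation 0.6 and Month 1 rates 79/44.1: imputed rates are 74.2% and 58.4% against true 79% and 44.1%. The difference is 15.8 points, and 15.8 / 34.9 = 45%. Control moves by 14.3 points and VOLBELLA by 4.8.

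**Step 2: share kept among imputed subjects, no arm term.**

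| Month 1 rates (assumed) | Arm term alone, obs. corr. 0.36–0.60 | Arm term alone, obs. corr. 0.67–0.79 | Linear, rounded and truncated, 0.36–0.60 | Proportional odds, 0.36–0.60 |
|---|---|---|---|---|
| 79 / 44.1 | 38–53% | 73% | 33–48% | 38–54% |
| 90 / 44.1 | 58–76% | 99% | 47–67% | 56–76% |
| 95 / 44.1 | 68–86% | 106% | 54–74% | 65–85% |
| 90 / 30 | 75–95% | 119% | 60–84% | 72–96% |

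The pull is usually toward zero. It vanishes or reverses when the Month 1 effect is larger than the Month 3 effect and the correlation is high.

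**Step 3: the scoring gap.** If linear imputed scores are compared with a 1-point gain without rounding, imputed responder rates are about 40–48% for VOLBELLA (true 79%) and 17–38% for control (true 44.1%), over latent correlations 0 to 0.9.

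**Step 4: with arm added, observed correlation 0.36–0.60.** Rounded linear keeps 72–79%, proportional odds 87–92%, and proportional odds fitted by arm 91–94%.

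**Step 5: a second set of assumptions.** Here the baseline mix is 30/40/30, the latent SD is 0.8 grade, the latent correlation runs from 0.3 to 0.9, and the model is rounded linear. The true difference among missing subjects is about 35 points. Without arm, the imputed difference is 10.5, 15.0, 20.6 and 26.6 points (correlation 0.3, 0.5, 0.7, 0.9) if Month 1 rates equal Month 3 rates. It is 16.7 to 39.9 points if Month 1 rates are 90/44.1 or 85/30. With arm it is 31.0 to 32.8 points in all 12 settings. When Month 3 was generated from baseline and Month 1 only, the two models agreed (27.5 without arm, 27.7 with, true 28.5), so the exception in the claim is genuine.

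**Step 6: the whole trial.**
- Upper bound, total loss among imputed: 34.9 × (1 − 0.15) = 29.7 points; 34.9 × (1 − 0.05) = 33.2 points.
- Arm term alone, largest pull in the table (38% kept): (1 − 0.38) × 34.9 × 0.15 = 3.2 points. Largest reversal (119% kept): 0.19 × 34.9 × 0.15 = 1.0 point.
- Simulated 132/44 trials with the linear rounded model, M = 5: shift from the observed-case difference of −3.6 to +0.5 points at 15% missing and −1.2 to +0.2 at 5%. This shift combines the missing arm term with the rounding loss.
- Fisher check at total loss: the pooled rate is 0.75 × 79 + 0.25 × 44.1 = 70.3%. The overall rates are 0.85 × 79 + 0.15 × 70.3 = 77.7% and 0.85 × 44.1 + 0.15 × 70.3 = 48.0%, that is 103/132 vs 21/44, p about 0.0002.

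**The case against.** The strongest reply is that no decision rests on this model. The primary test uses observed cases, the imputation is sensitivity-only, and LOCF and PP do not depend on it. That stands, and it limits the weight of the point.

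The exposed group is also small. Protocol 8.5 reaches 15% by "Allowing for attrition of 15% up to month 3 due to early discontinuations, missed visits, or out-of-analysis-window visits". The SAP's Month 3 windows are wide (Days 62 to 136 for treated subjects; Day 62 to exit or optional treatment for controls), and mITT drops subjects with no post-baseline LFS. So 15% is an upper bound, and this also stands.

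The size depends on inputs the documents do not give. With kept shares from 38% to 119%, neither size nor direction is fixed. That is true. But an analysis whose bias can go either way by an unknown amount cannot be defended as conservative.

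The whole-trial simulation mixes two faults. This is fair, so the arm-only figure of 3.2 points is given beside it.

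The preference for an ordinal model is less secure than the need for an arm term. Rounded linear with arm kept 72–79% under the first assumptions but 31.0–32.8 of about 35 points, roughly 89–94%, under the second, where the ordinal form was not tested. Still, under the first assumptions rounded linear with arm can do worse than without it (78% vs 84% kept at Month 1 rates 90/30, latent correlation 0.7), which supports the ordinal choice.

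Finally, the unrounded-threshold figures take the most adverse reading of the missing rule. They show why the rule must be written, not what a programmer would necessarily do.

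**Conclusion.** The concern holds. The printed model is complete and omits arm, so it gives a wrong arm contrast among imputed subjects unless Month 1 LFS carries the whole arm effect. In the assumed scenarios the missing term keeps 38–95% of the 34.9-point difference among imputed subjects at observed correlation 0.36–0.60, and 73–119% at 0.67–0.79.

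At trial level this is a matter of a few points at most: about 3 points from the arm term alone at 15% missing, and about 5 points (34.9 to 29.7) if the whole difference were lost among imputed subjects. At the planned rates superiority survives even then, and the primary analysis is untouched. The point should be corrected, but it does not threaten the trial's main conclusion. Confidence in the fault itself is high. Confidence in its size is moderate, because Month 1 rates, correlation, the distribution of grade changes and the missingness pattern are all assumed.

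**What to change.** In SAP Table 5-3, before database lock:

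1. Add treatment arm to the imputation model, or run the imputation separately by arm. This is the essential change.
2. Name the model type. Preferably impute on the ordinal 0–4 scale with a proportional-odds model; otherwise state that imputed scores are rounded and truncated to 0–4 before responder status is derived.
3. While the table is open, say what is done when Month 1 LFS is also missing, since the model needs it and the SAP is silent.

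The cost is SAP wording and a few lines of code. No new data are needed, and the primary analysis does not change.

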8.3.1 Primary Effectiveness Analyses

The primary effectiveness analysis will test for superiority of VOLBELLA with Lidocaine over no treatment in the difference in overall lip fullness responder rate based on the Evaluating Investigator's assessment at month 3. Month 3 refers to 3 months after the last treatment for subjects in the VOLBELLA with Lidocaine group and 3 months after randomization for subjects in the no-treatment control group.

The null hypothesis is that the responder rate for VOLBELLA with Lidocaine group is equal to the responder rate for the no-treatment control group. The alternative hypothesis is that the responder rates are not equal for the VOLBELLA with Lidocaine and the no-treatment control groups. These hypotheses are stated as:

$$H_0: P_v - P_c = 0$$

$$H_a: P_v - P_c > 0 \text{ or } P_v - P_c < 0$$

where P_v and P_c denote the responder rates for the VOLBELLA with Lidocaine group at month 3 after last treatment and no-treatment control group at month 3 after randomization, respectively. Two-sided Fisher's exact test with 5% significance level will be used to compare treatment effects between VOLBELLA with Lidocaine and the no-treatment control group. If the 2-sided p-value is less than 0.05 and the responder rate is greater for VOLBELLA with Lidocaine than for the no-treatment control group, then VOLBELLA with Lidocaine will be considered superior to the no-treatment control group. The primary effectiveness analysis will be performed on the mITT population.

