CFB Wilcoxon test	
 
• Continuous descriptives for baseline, postbaseline, and CFB values
 
• For comparing VOLBELLA group vs. no-treatment control group during UCP (Volbella minus control)               
 
◦ Mean differences
 
◦ P-values and 95% CI from Wilcoxon rank-sum test
 
 
 
• N included = subjects with non-missing values at both baseline and the specified postbaseline analysis visit
 

Responder exact test	
 
• Categorical descriptives for responders
 
• Exact binomial 95% CI of percentages within group
 
• For comparing VOLBELLA group vs. no-treatment control group during UCP (VOLBELLA minus control)               
 
◦ Responder rate difference
 
◦ 95% exact unconditional confidence interval
 
◦ P-value from 2-sided Fisher's exact test
 
 
 
• N included = with non-missing values at both baseline and the specified postbaseline analysis visit
 

Responder exact 95% CI within group (treatment group only)	
 
• Categorical descriptives for responders
 
• Exact binomial 95% CI of percentages within group
 
• N included = with non-missing values at both baseline and the specified postbaseline analysis visit
 

Responder CMH	
 
• Categorical descriptives for responders
 

Methodology	Description
test	
 
• Responder rate differences for VOLBELLA group vs. no-treatment group during UCP
 
• P-values from Cochran-Mantel-Haenszel test stratified by baseline characteristic comparing VOLBELLA group vs. no-treatment group during UCP
 
• N included = with non-missing values at both baseline and the specified postbaseline analysis visit
 

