**Table 5-24 Sample Size Assumptions**

Parameter	Assumption / Estimate
Primary endpoint	Lip fullness assessment responder
Risk difference 	34.1% (79% Volbella vs 44.1% Control)
SD	NA
$\alpha$	5%
Sides	2
Power	$>$ 96%
N per group	111 in treatment group, 37 in no-treatment control group
Drop-out Rate	15%
N total randomized	176

 Based on interim data from Study JULIDO-002.

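### The multiple-imputation sensitivity analysis fits a linear equation without an arm term to a five-grade score, then applies a one-grade cut; rounding and pooling are left unstated, so imputed response is misstated whether or not draws are rounded.

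*SAP*

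**What the plan says.** SAP Table 5-3 gives two ways of handling a missing Month 3 LFS, both for sensitivity analysis of the primary endpoint only: multiple imputation and last observation carried forward. For the first it states "Multiple imputation with 5 imputed datasets is applied to subjects with Month 3 LFS missing using the below model". The equation printed there sets Month 3 LFS equal to an intercept plus one coefficient each for baseline LFS and Month 1 LFS. It shows no link function, error term, rounding step or treatment-arm term.

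The imputed variable is a grade. Protocol Table 4 scores LFS 0, 1, 2, 3 or 4. Under SAP 5.1.3.1 a "responder is defined as a subject with at least one grade improvement from baseline on 5-point LFS".

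The one method that Table 5-15 assigns to this endpoint is the Responder exact test. Table 5-2 defines it by a within-arm exact interval, a responder-rate difference, an exact unconditional interval for that difference, and a "P-value from 2-sided Fisher's exact test". For the sensitivity analysis, SAP 5.1.3.1 refers back to the missing-data conventions and to the PP population. It names no test for the imputed datasets and no rule for combining them.

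**The concern.** An observed subject who gains one grade sits exactly on the responder cut. A decimal drawn around a predicted gain of one grade falls below that cut about half the time. Left as decimals, imputed values therefore turn many would-be responders into non-responders for a purely numerical reason.

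Rounding removes most of that problem but exposes another. The equation has no arm term, so Month 1 LFS alone carries the treatment effect into the imputation. Controls are then imputed largely from a relationship fitted to treated subjects, who outnumber them three to one.

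At stake is one of only two imputation checks on the primary result. Its answer would depend on a programming choice that the SAP does not fix and that could be made after the data are seen. Subjects know their assignment (Protocol 4.3.3), so unequal missingness between arms is possible, and with it a shift in the arm difference.

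**Working it through.** **Inputs from the documents.** Responder rates "79% Volbella vs 44.1% Control" and evaluable numbers "111 in treatment group, 37 in no-treatment control group" (SAP Table 5-24); 132 + 44 randomized and 15% attrition to Month 3 (Protocol 8.5); five imputations and the printed equation (SAP Table 5-3).

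**Assumptions not in the documents.** The share of treated subjects gaining two grades (0-40%), the Month 1-Month 3 correlation (0.6 to 0.85) and the baseline grade mix.

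**1. The plan's own figure.** Protocol 8.5 says the sample size "will provide > 96% power to detect the superiority". Summing the probabilities of all pairs of binomial outcomes (111 at 79.0%, 37 at 44.1%) with two-sided Fisher p < 0.05 and the treated rate higher gives 96.7%, which agrees. The planned difference is 79.0 − 44.1 = 34.9 points. Table 5-24 prints 34.1, but the power matches the two rates, so 34.9 is used here.

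**2. Effect of the cut, each arm taken alone.** Treat the imputed change as normal with the mean and SD of the true grade change. P(response) = 1 − Φ((c − mean)/SD), with c = 1 unrounded and c = 0.5 rounded.

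| Assumed changes | Mean | SD | Unrounded | Rounded | True |
|---|---|---|---|---|---|
| Treated: 21% 0, 79% +1 | 0.79 | 0.407 | 30% | 76% | 79% |
| Treated: 21% 0, 39% +1, 40% +2 | 1.19 | 0.758 | 60% | 82% | 79% |
| Control: 55.9% 0, 44.1% +1 | 0.441 | 0.497 | 13% | 45% | 44.1% |

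**3. The equation as printed (no arm term).** Simulated trials of 132 + 44 subjects, 15% missing at random, proper normal-regression imputation with five datasets, 600 runs per setting. Response among imputed subjects:
- unrounded: about 28-59% treated, 17-35% control;
- rounded: about 68-79% treated, 51-61% control;
- rounded with an arm term added: about 75-81% treated, 45-49% control.

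The low end of the unrounded treated range arises when changes are only 0 or +1, the high end when 40% of treated subjects gain two grades.

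**4. Whole-trial effect.** Overall rate = (1 − m) × true rate + m × imputed rate, where m is the fraction missing.
- 15% in both arms, unrounded, low case: treated 0.85 × 0.79 + 0.15 × 0.29 = 0.715; control 0.85 × 0.441 + 0.15 × 0.19 = 0.403; difference 31.2 points. The most favourable simulated case is 76.1 − 41.6 = 34.5. Range: about 31-35.
- 15% in both arms, rounded, one case: 0.85 × 0.79 + 0.15 × 0.705 = 0.777; 0.85 × 0.441 + 0.15 × 0.566 = 0.460; difference about 32.
- 20% treated and 5% control missing (assumed), unrounded: 0.80 × 0.79 + 0.20 × 0.28 = 0.688 and 0.95 × 0.441 + 0.05 × 0.19 = 0.428, difference 26.0; with imputed rates of 57% and 34%, 0.746 − 0.436 = 31.0. Simulation: 26-31.
- 5% treated and 20% control missing (assumed), same imputed rates: 0.7645 − 0.3908 = 37.4 and 0.779 − 0.421 = 35.8. Simulation: 36-38.

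**5. Would the conclusion change?** Fisher p at expected counts in 132 and 44 subjects: no bias, 104 vs 19, p = 0.00002; unrounded low case, 94 vs 18, p = 0.0005; rounded case, 103 vs 20, p = 0.0001. Power of a pooled Wald test in the unrounded runs stayed at about 97-98%.

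**6. Pooling.** Rubin's rules need an estimate and a variance from each dataset: total variance = mean within-dataset variance + (1 + 1/5) × between-dataset variance. A Fisher p-value with an exact interval supplies no variance. The responder-rate difference does, in large samples: p₁(1 − p₁)/n₁ + p₂(1 − p₂)/n₂.

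**The case against.** The strongest reply is that this is an omission, not an error. Table 5-3 prints only a linear predictor, which could be shorthand for an ordinal model or could be followed by rounding. That reply stands in part: a reader might infer that imputed response must be far too low in both arms, but this holds only if draws are left as decimals, and the SAP is silent on that. It does not remove the point, because rounding under the printed equation leaves the control rate too high. A cumulative logistic model would also need a link and several intercepts, and the equation shows one intercept and no link.

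A reader might also infer that the five results cannot be combined. The documents do not support that: the Responder exact test row lists the rate difference, which can be pooled with a large-sample variance. Nor does the SAP prescribe Fisher's test for imputed data; that is an inference from the primary method. What stands is that no test and no combining rule are stated.

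Finally, the impact is limited. The 15% in Protocol 8.5 is a high figure for this analysis, because mITT already requires at least one post-baseline LFS. The Month 3 window is wide: Days 62-136 for treated subjects, and Day 62 to exit or optional treatment for controls. That makes heavy control missingness, the pattern that would inflate the effect, harder to reach. All of this stands and limits how serious the point is.

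**Conclusion.** The point holds at moderate weight. The printed model suits neither the scale nor the responder rule, and it misstates imputed response whether or not draws are rounded. How far depends on assumed change distributions and an assumed Month 1-Month 3 correlation, so the figures above are ranges. With 15% missing in both arms the arm difference moves by at most about 4 points, downward, and significance at the planning rates is not threatened. The larger shifts need missingness of 20%/5% or 5%/20%, for which the documents give no basis.

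A reader might infer that the trial's main conclusion is at risk. It is not: the primary analysis uses no imputation, and the carried-forward check uses whole grades. The weakness is confined to one sensitivity analysis, which as specified cannot be run to a single, reproducible answer.

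**What to change.** In SAP Table 5-3, replace the linear equation with an ordinal (cumulative) logistic model for Month 3 LFS, or a logistic model for the responder indicator. Include baseline LFS, Month 1 LFS and treatment arm, or impute separately by arm. In each imputed dataset estimate the responder-rate difference and its standard error, and pool by Rubin's rules into one estimate, confidence interval and p-value. Add a matching row to Table 5-2 so that the method is named. Keep Fisher's exact test for the unimputed primary analysis, where Protocol 8.3.1 says "Two-sided Fisher's exact test with 5% significance level will be used".

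The cost is SAP wording before database lock and a little code. The sensitivity p-value will rest on a large-sample approximation and will no longer be exact. Sample size, study conduct and the primary test do not change.
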